#### 1 BACKGROUND AND RATIONALE

Head and neck cancers are among the most common cancers worldwide, accounting for more than 550,000 cases and around 300,000 deaths each year, and these trends are increasing. In the United States, there were ~45,780 new cases of oral cavity and pharynx cancer and ~8,650 people were expected to die of this disease in 2015. Approximately 90% of all head and neck cancers are squamous cell carcinomas. Most SCCHNs arise from the epithelial lining of the oral cavity, oropharynx, larynx and hypopharynx. The most important risk factors identified in SCCHNs, include tobacco and alcohol use, and, in a subgroup of SCCHNs (particularly oropharynx tumors), human papillomavirus (HPV) as a strong independent prognostic factor, with HPV positive-infected tumors associated with more favorable clinical outcomes.

The treatment approach and prognosis for patients with SCCHN is mostly determined by the tumor stage at presentation. About one-third of patients present with early stage disease, whereas the majority present with advanced disease with lymph node metastasis. With standard of care treatment, the 5-year survival for localized oral cavity and pharynx cancer is 83%, but survival drops to 37.7% for metastatic disease Approximately half of the treated population returns with recurrent or refractory disease, and for these patients, the 1-year survival rate ranges from 5% to 33% with a median overall survival (OS) of 6 to 9 months. Recurrent disease that is not amenable to curative-intent radiation or surgery have the same treatment approach as metastatic disease, and participation in a clinical trial is a recommended treatment option for these patients. A Phase 3 randomized trial in first-line recurrent or metastatic (1L R/M) SCCHN showed that cetuximab plus platinum-fluorouracil chemotherapy (EXTREME regimen) improved survival over platinumfluorouracil alone as first-line treatment with a median OS of 10.1 months versus 7.4 months (Hazard Ratio [HR] = 0.80, 95% CI 0.64-0.99, p = 0.04). As a result, the EXTREME regimen has been adapted as a standard treatment approach in this population. While the addition of cetuximab to platinum-fluorouracil chemotherapy improved response rates and disease control rates, the duration of response did not differ significantly between treatment regimens. Since the introduction of the EXTREME regimen in 2008, 4 no marked improvement in survival has been achieved, with patients still frequently developing recurrences and distant metastasis. After progression, the limited treatment options available are associated with substantial morbidity and mortality. Thus, new treatment approaches need to be explored as the first-line treatment in this population.

Checkmate  $141^6$  showed that nivolumab monotherapy, as a second line therapy (2L) in R/M SCCHN, increased the length of time patients lived when compared with standard, single agent chemotherapy in in all study participants (HR = 0.68, 95% CI 0.54 to 0.86; p = 0.01).

Preclinical data indicate that the combination of PD-1 and CTLA-4 receptor blockade may improve antitumor activity. In vitro combinations of nivolumab plus ipilimumab increase IFN-γ production 2- to 7-fold over either agent alone in a mixed lymphocyte reaction. Increased antitumor activity of the combination was also observed in 3 of 5 syngeneic murine cancer models. In a murine melanoma vaccine model, blockade with either CTLA-4 or PD-1 antibodies increased the proportion of

CTLA-4 and PD-1-expressing CD4/CD8 tumor infiltrating T effector cells, and dual blockade increased tumor infiltration of T effector cells and decreased intratumoral T regulatory cells, as compared to either agent alone.

The combination of ipilimumab with nivolumab showed increased activity versus nivolumab alone in multiple tumor types, including melanoma, multiple types of lung cancer, gastric cancer, and renal cancer.

Given the similarity in patient profiles of NSCLC and SCCHN, this study will evaluate the efficacy and safety profile of the combination of ipilimumab with nivolumab as first-line therapy in recurrent or metastatic squamous cell carcinoma of the head and neck (SCCHN).

#### **Research Hypothesis:**

- Subjects with PD-L1 Combined Positive Score (CPS) ≥ 20 who receive nivolumab in combination with ipilimumab for first-line treatment of recurrent or metastatic SCCHN will have longer OS than comparable subjects who receive the EXTREME regimen
- Subjects who receive nivolumab in combination with ipilimumab for first-line treatment of recurrent or metastatic SCCHN will have longer OS than comparable subjects who receive the EXTREME regimen

#### **Schedule of Analyses:**

A formal interim analysis for superiority of OS will be performed after approximately 593 OS events (out of 741 required, 80%) have occurred on all randomized subjects or all randomized subjects have been followed up for at least 12 months, whichever is later. An interim analysis for superiority of OS for subjects with PD-L1 CPS  $\geq$  20 will be performed simultaneously. An independent statistician external to BMS will perform these analyses.

Final analysis of OS will be conducted when approximately 741 events have occurred on all randomized subjects across the two treatment arms.

#### 2 STUDY DESCRIPTION

#### 2.1 Study Design

Protocol CA209651 is a randomized open-label, Phase 3 trial in subjects ≥ 18 years old with untreated metastatic or recurrent SCCHN that is not amenable to curative therapy, evaluating nivolumab + ipilimumab versus the EXTREME regimen (cetuximab + cisplatin/carboplatin + fluorouracil) as a first-line treatment.

Subjects will undergo screening evaluations to determine eligibility prior to randomization. Approximately 930 subjects will be randomized to the two treatment arms in a 1:1 ratio and stratified by the following factors:

• Tumor cell PD-L1 status (expressing [≥ 1%] vs non-expressing [< 1%] or non-evaluable). Up to 10% of randomized subjects per cohort can be included into the study as "non-evaluable." After this point, subjects with non-evaluable results will not be permitted to be randomized; the site would need to submit an additional tumor tissue for testing with either a result of "expressing" or non-expressing" in order to randomize the subject.

- HPV p-16 status (oropharyngeal HPV p-16 positive vs oropharyngeal HPV p-16 negative or non-oropharyngeal).
- Prior chemotherapy (adjuvant/neoadjuvant/multimodal treatment) status (Yes/No)

The dose and treatment schedules for each arm are as follows:

- Arm A: Nivolumab + Ipilimumab Arm:
  - Nivolumab 3 mg/kg IV every 2 weeks + Ipilimumab 1 mg/kg IV every 6 weeks until progression, unacceptable toxicity, or a maximum of 24 months from first study treatment.
- Arm B: EXTREME regimen Arm:
  - Cetuximab 400 mg/m² IV for the initial dose only, then 250 mg/m² weekly + cisplatin (100 mg/m²) or carboplatin (AUC of 5 mg per milliliter per minute) on Day 1 and fluor-ouracil (1000 mg/m² per day for 4 days) every 3 weeks for maximum of 6 cycles followed by maintenance cetuximab at 250 mg/m² weekly (or every 2 weeks, per local prescribing information) until disease progression or unacceptable toxicity; the choice of cisplatin or carboplatin is at the discretion of the investigator.

Tumor progression or response will be assessed by investigator using RECIST 1.1 criteria. Treatment with study medication will continue until RECIST 1.1 defined progression, unacceptable toxicity, a maximum of 24 months from the first study treatment, or withdrawal of consent.

Dose reductions will be not be allowed for nivolumab or ipilimumab.

Treatment beyond initial investigator-assessed progression (either clinical or radiographical) is permitted for nivolumab and ipilimumab if the subject has an investigator-assessed clinical benefit and is tolerating study drug.

[figure not shown]
In addition to investigator assessment of response and progression, there will be a blinded independent central review (BICR) of tumor scans and study sites will need to submit tumor scans for central radiology review.

A DMC will be established and meet regularly during the study to ensure that subject safety is carefully monitored and to provide oversight regarding safety and efficacy considerations in protocol CA209651.

The maximum duration of the study from start of randomization to final analysis of OS is projected to be 51 months, assuming 26 months accrual duration. Additional survival follow-up may continue for up to 5 years from the time of this analysis. The study will end once survival follow-up has concluded.

The study design schematic is presented in Figure 2.1-1.

Figure 2.1-1: Study Design Schematic

#### 2.2 Treatment Assignment

This is an open label, randomized, Phase 3 trial in subjects  $\geq$  18 years old with untreated metastatic or recurrent SCCHN that is not amenable to curative therapy.

Subjects in each arm will be stratified by:

- Tumor cell PD-L1 status (expressing  $[\ge 1\%]$  vs non-expressing [< 1%] or non-evaluable)
- HPV p-16 status (oropharyngeal HPV p-16 positive vs oropharyngeal HPV p-16 negative or non-oropharyngeal)
- Prior chemotherapy (adjuvant/neoadjuvant/multimodal treatment) status (Yes/No)

Subjects will be randomized in 1:1 and treated with one of open-label treatments Arm A or Arm B.

#### 2.3 Blinding and Unblinding

This is an open label study. However, the sponsor is strictly prohibited from looking at unblinded aggregate efficacy data while the study is still ongoing. The sponsor is forbidden from looking at data by arm while the study is ongoing.

#### 2.4 Protocol Amendments

Table 2.4-1: Protocol Amendments

Document	Date of Issue	Summary of Changes
Revised Protocol 05	19-Dec-2020	
 
Removed second interim analysis of OS.
 
Added a Myocarditis adverse event management algorithm.
 

Revised Protocol 04	20-Jun-2019	
 
The primary objectives were changed to compare:         
 
OS for subjects who are receiving nivolumab + ipilimumab versus EXTREME regimen in subjects with PD-L1 CPS ≥ 20 (changed from tumor PD-L1 ≥ 1) and
 
OS for subjects who are receiving nivolumab + ipilimumab versus
 
 
 

**Table 2.4-1:** Protocol Amendments

Document	Date of Issue	Summary of Changes
		EXTREME regimen in all study subjects (irrespective of PD-L1 expression).
		
 
Description of the statistical analyses were changed based on the changes in objectives
 

		
 
Key secondary objective was changed to OS in subject with PD-L1 CPS ≥ 1.
 

		
 
Efficacy evaluation based on biomarker subgroups were added to exploratory objectives.
 

		Added supporting data for change in objectives from recent years and updated literature references
		
 
Updated protocol to align with current standards for BMS clinical studies.
 

		Minor formatting and typographical corrections.
		
 
The primary objectives were changed from PFS and OS in all ran- domized subjects to PFS and OS in subjects with PD-L1 expressing tumors.
 

		
 
PFS and OS in all study subjects moved to secondary endpoints.
 

		• The hierarchy for the analysis was updated -PFS in all study subjects would be tested hierarchically after PFS in subjects with PD-L1 expressing tumors. OS in all study subjects would be tested hierarchically after OS in subjects with PD-L1 expressing tumors.
Revised Protocol 03	01-May-2018	
 
The sample size was increased to allow for evaluation of the updated primary end-points. The sample size determination was updated ac- cordingly.
 

		
 
Added brief description of the analysis of TMB data.
 

		• Change in medical monitor and study director for the study (Administrative Letter 04 (date of issue:20-Mar-2018))
		
 
Added that nivolumab should be permanently discontinued in case of grade 3 drug-related myocarditis.
 

		
 
Minor formatting and typographical corrections.
 

		The sample size was increased.
		• A maximum duration of nivolumab and ipilimumab treatment of 24 months from the start of treatment was added.
Revised Protocol 02	26-Oct-2017	
 
Duration of response has been changed from an exploratory objective to a secondary objective based on the expected improvement induration of response as seen in other nivolumab trials. Response to first therapy after disease progression was changed to an exploratory endpoint to limit the secondary objectives only to critical endpoints.
 

		
 
Exploratory biomarker objectives were added in order to evaluate the potential associations between efficacy outcomes (such as objec- tive response rate, PFS, and OS) with select biomarkers, including tumor mutational burden, from tumor tissue and peripheral blood.
 

Administrative Letter 03	06-Oct-2016	Change in medical monitor.
Administrative	14-Sep-2016	Change to section 5.8, Additional Research section modified.

Document	Date of Issue	Summary of Changes
Letter 02		
Revised Protocol 01	22-Jun-2016	Incorporates Amendment 02
Amendment 02	22-Jun-2016	Week 7 biopsy optional instead of required, Section 5.8 "Additional Research" added, PK and IMG Follow up visit samples no longer required to be collected, Radiographic Imaging wording updated for clarification. Updated Algorithms for Renal, Pulmonary and Skin to match with updated Nivolumab IB v15 (includes Nivo IB 15 erratum update). Other minor edits, clarifications, corrections.
Original Protocol	23-Mar-2016	Not applicable

Table 2.4-1: Protocol Amendments

#### 2.5 Data Monitoring Committee

A Data Monitoring Committee (DMC) will be utilized to provide general oversight and safety considerations for this study. The DMC will provide advice to the Sponsor regarding actions the committee deems necessary for the continuing protection of subjects enrolled in this study. The DMC will be charged with assessing such actions in light of an acceptable risk/benefit profile for nivolumab. The DMC will act in an advisory capacity to BMS and will monitor subject safety data for the study.

The DMC will be advisory to the clinical study leadership team. The clinical study leadership will have responsibility for overall conduct of the study including managing the communication of study data. The group will be responsible for promptly reviewing the DMC recommendations, for providing guidance regarding the continuation or termination of the study, and for determining whether amendments to the protocol or changes to the study conduct are required.

Details of the DMC responsibilities and procedures are specified in the DMC charter.

# 2.6 Blinded Independent Central Review (BICR)

A BICR will be employed for interpretation of radiographic progression events. At the time of investigator-assessed initial radiographic progression per RECIST 1.1 criteria in any given subject, the site must request the independent central review from the third party radiology vendor for confirmation of progression.

Tumor assessments for each subject should be submitted to the radiology vendor as they are performed on an ongoing basis. The blinded, independent radiologists will review all available tumor assessments for that given subject and determine if RECIST 1.1 criteria for progression have been met. The independent assessment of whether or not the given subject met criteria for progression will be provided to the site. Subjects whose disease progression is not confirmed centrally will be

\* Other protocol amendments are site specific and did not require protocol to be updated.

required to continue treatment and tumor assessments according to the protocol-specified schedule. Subsequent tumor assessments must be submitted to the third party radiology vendor for subsequent review and may be discontinued when the investigator and independent radiologists both assess the subject to have met criteria for progression.

The BICR will also review tumor images in all randomized subjects to determine RECIST 1.1 best overall response for the analyses of ORR.

At time of analysis of ORR, tumor assessments will use BICR in all randomized subjects to determine progression and response for the analyses of PFS and ORR. Details of the BICR responsibilities and procedures will be specified in the BICR charter.

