Tumor progression or response will be assessed by investigator using RECIST 1.1 criteria. Treatment with study medication will continue until RECIST 1.1 defined progression, unacceptable toxicity, a maximum of 24 months from the first study treatment, or withdrawal of consent. See [Section 3.5](#) for full details of discontinuation of study drug treatment.

Dose reductions will not be allowed for nivolumab or ipilimumab.

Treatment beyond initial investigator-assessed progression (either clinical or radiographical) is permitted for nivolumab and ipilimumab if the participant has an investigator-assessed clinical benefit and is tolerating study drug (see [Section 4.5.6](#)).

[figure not shown]
In addition to investigator assessment of response and progression, there will be a blinded independent central review (BICR) of tumor scans and study sites will need to submit tumor scans for central radiology review.

A DMC will be established and meet regularly during the study to ensure that participant safety is carefully monitored and to provide oversight regarding safety and efficacy considerations in protocol CA209651.

The maximum duration of the study from start of randomization to final analysis of OS is projected to be 51 months, assuming 26 months accrual duration. Additional survival follow-up may continue for up to 5 years from the time of this analysis. The study will end once survival follow-up has concluded.

The study design schematic is presented in Figure 3.1-1.

Figure 3.1-1: Study Design Schematic

This study will consist of 3 phases: screening, treatment, and follow-up.

Screening Phase

- Begins by establishing the participant's initial eligibility and signing of the informed consent (ICF).
- Participant is enrolled using the Interactive Voice Response System (IVRS).
- Tumor tissue (archival or recent tumor biopsy) must be submitted by the site to a Central Lab for determination of tumor cell PD-L1 status. For this study we will use PD-L1 stained with the DAKO 28-8 antibody. Additional tumor tissue may be required by Central Lab if initial testing is unevaluable.
- HPV p-16 status must be available prior to randomization. If it is not available locally, then this will need to be tested by central lab, and the results need to be known prior to randomization. See [Section 5.6.8](#).

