4.5.6 Treatment Beyond Disease Progression (Arm A only)

Accumulating evidence indicates a minority of participants treated with immunotherapy may derive clinical benefit despite initial evidence of PD.

Participants will be permitted to continue on nivolumab combined with ipilimumab for treatment beyond initial RECIST 1.1 defined PD up to a total of 24 months total treatment duration from the start of study treatment as long as they meet the following criteria:

- Investigator-assessed clinical benefit and no rapid disease progression
- Participant is tolerating study treatment
- Stable performance status
- Treatment beyond progression will not delay an imminent intervention to prevent serious complications of disease progression (eg, CNS metastases)
- **Participant** provides written informed consent prior to receiving additional nivolumab and ipilimumab treatment, using an ICF describing any reasonably foreseeable risks or discomforts, or other alternative treatment options.

The decision to continue treatment beyond initial investigator-assessed progression should be discussed with the BMS Medical Monitor and documented in the study records. A follow-up scan should be performed within six (6) weeks \pm 1 week of original PD to determine whether there has been a decrease in the tumor size, or continued progression of disease. Subsequent scans should be performed every six (6) weeks \pm 1 week until further progression is determined. In the event of unscheduled scans, efforts should be made to get subsequent scan back on the every six (6) weeks \pm 1 week until further progression is determined.

If the investigator feels that the participant continues to achieve clinical benefit by continuing treatment, the participant should remain on the trial and continue to receive monitoring according to the Time and Events Schedule in [Table 5.1-2](#).

For the participants who continue study therapy beyond progression, further progression is defined as an additional 10% increase in tumor burden from time of initial PD. This includes an increase in the sum of diameters of all target lesions and/ or the diameters of new measurable lesions compared to the time of initial PD. Nivolumab and ipilimumab treatment should be discontinued permanently upon documentation of further progression.

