Tumor Biopsy Sample:	X	
Tumor biopsy specimens will be obtained from consenting participants within all treatment arms at Week 7 and once disease progression has been documented (See Table 5.6-1). Biopsy should be excisional, incisional or core needle (fine needle aspiration is insufficient) and submitted to central lab see also Table 5.6-1

Table 5.1-2: On Treatment Procedural Outline (All Treatments) CA209651 (All Cohorts)

Procedure	During Treatment Visit ^{a,b}	Notes
Saliva Sample: Oral microbiome	X	See Table 5.6-1
Clinical Drug Supplies		
IVRS Drug Vial Assignment	X	
Dispense Study Drug	X	Within 3 days from randomization, the participant must receive the first dose of study medication.

^a For Ipilimumab/Nivolumab Arm: Visits occur every 2 weeks

^b For EXTREME regimen Arm: Visits occur every 3 weeks

Table 5.1-3: Follow-Up Period (all treatment groups)

Procedure	Follow Up, Visits 1 and 2 ^a	Survival Follow-Up Visits ^b	Notes
Safety Assessments			
Targeted Physical Examination	X		To assess for potential late emergent study drug related issues.
Vital Signs	X		
Adverse Events Assessment	X		In survival period only to include toxicities from study therapy.
Review of Concomitant Medication	X	X	Document Subsequent Cancer Therapy
Laboratory Tests	X		CBC w/ differential, LFTs, BUN or serum urea level, creatinine, Ca, Mg, Na, K, Cl, LDH, phosphate, glucose, amylase, lipase. TSH (+ reflex Free T4 and Free T3 collected ONLY if TSH is abnormal). To be done at FU1, to be repeated at FU2, if study related toxicity persists.
Pregnancy Test (WOCBP only)	X		Serum or urine.
Efficacy Assessments			
Tumor Assessment	X	X	Only for participants without progression. - Tumor assessments should occur every 6 weeks (\pm 1 week) for the first 48 weeks, then every 12 weeks (\pm 1 week) until disease progression or treatment is discontinued (whichever occurs later). - CT or MRI of the neck, chest, abdomen, pelvis and all known sites of disease. Use same imaging method as was used at screening/baseline. - MRI of the brain (without AND with Gadolinium contrast) is required for participants with a history of brain metastasis. Note: MRI of the brain is preferred but CT scan is acceptable. Surveillance scans should be performed approximately every 12 weeks, or sooner if clinically indicated. (CT of the head without AND with contrast may be performed if MRI is contraindicated).
Outcomes Research Assessment			
FACT-H&N	X		Can be collected over the phone.

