Tumor assessments for all participants should continue as per protocol even if dosing is delayed or discontinued. Tumor measurements should be made by the same investigator or radiologist for each assessment whenever possible. Change in tumor measurements and tumor response to guide ongoing study treatment decisions will be assessed by the Investigator using the RECIST 1.1 criteria ([Appendix 3](#)).

All radiographic assessments performed for study purposes will be submitted to the third-party radiology vendor for central review. Tumor assessments should be submitted to the third-party radiology vendor as they are performed on an ongoing basis.

At the time of investigator-assessed off-treatment disease progression, the site must complete the tumor assessment pages in TAO documenting disease progression and submit a fresh biopsy sample of metastatic site to Central Lab for biomarker analysis as specified in [Section 5.6.3](#).

In addition, participants receiving nivolumab and ipilimumab treatment beyond progression must continue tumor assessments until such treatment has been discontinued.

Refer to the study Imaging Manual for further guidance on obtaining and submitting study related scans.

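### SAP 2.6 requires treatment and scans to continue when central review does not confirm progression, but the protocol and SAP 2.1 have no such step; BICR PFS and DOR may be informatively censored if sites follow the protocol

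*SAP*

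**What the plan says.** **SAP 2.6.** When an investigator first assesses radiographic progression in any subject, the site must ask the radiology vendor for central confirmation. "The independent assessment of whether or not the given subject met criteria for progression will be provided to the site". Subjects not confirmed centrally are "required to continue treatment and tumor assessments according to the protocol-specified schedule". Later scans go on being submitted and "may be discontinued when the investigator and independent radiologists both assess the subject to have met criteria for progression". No arm is exempted.

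**Protocol.** Section 3.1 states: "Tumor progression or response will be assessed by investigator using RECIST 1.1 criteria". It adds: "Treatment with study medication will continue until RECIST 1.1 defined progression", or until toxicity, the 24-month limit or withdrawal of consent. Section 5.4 says that "tumor response to guide ongoing study treatment decisions will be assessed by the Investigator using the RECIST 1.1 criteria". BICR appears only as an additional review of submitted scans. Section 4.5.6 allows treatment beyond progression in Arm A alone, subject to clinical benefit, tolerance, stable performance status and written consent. In Table 5.1-3 the follow-up scans carry the note "Only for participants without progression".

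**SAP 2.1** repeats the protocol's investigator-based rule, so the SAP also disagrees with itself.

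**Analysis.** BICR is the assessor for the principal PFS analysis (protocol 5.4.2, SAP 7.5). SAP 7.5.5 plans a cross-tabulation of BICR against investigator PFS by arm, a concordance rate and a listing. It plans no hazard ratio for investigator-assessed PFS.

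**The concern.** Two matters are at stake.

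The first is consistency. The protocol and SAP describe different rules for when treatment and scanning end, so it is unclear which data the trial will generate.

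The second is the interpretation of BICR PFS and DOR. If scanning stops when the investigator calls progression and the central reader has not yet done so, no later scan exists on which BICR could record the event. Such a participant may be censored at a time closely linked to imminent progression, which breaks the independent-censoring assumption behind the Kaplan-Meier and Cox estimates. The trial is open label, and only Arm A participants may continue treatment and scans past progression, so the loss of scans may differ by arm.

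**Working it through.** The documents give no figure on this point to reproduce, so the check is mainly a comparison of texts.

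**Step 1. The rules side by side, after investigator progression that BICR does not confirm**

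| Question | SAP 2.6 | Protocol and SAP 2.1 |
|---|---|---|
| Central confirmation requested? | Yes, result returned to site | No such step |
| Treatment, Arm B | Required to continue | Ends at RECIST 1.1 progression; no provision to continue |
| Treatment, Arm A | Required to continue | Permitted if the conditions of 4.5.6 are met |
| Scans | Until both readers call progression | Until progression or end of treatment, whichever is later (5.4); off treatment, only without progression (Table 5.1-3) |

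The Arm B rows are incompatible. In Arm A the difference is between permitted and required. The protocol's scan-stopping sentences do not name the assessor; that it is the investigator follows from 3.1 and 5.4.

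**Step 2. What happens to BICR PFS if the protocol rule is followed.** Take a participant with investigator but not BICR progression who stops treatment and scans (SAP 4.2.2.1 and 4.2.2.2):

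- Dies with no new therapy: an event at death under both PFS definitions.
- Starts new therapy, then dies: censored at the last evaluable scan on or before the new therapy under the primary definition; an event at death under the secondary definition.
- Still alive at cutoff: censored under both definitions, at the last evaluable scan (under the primary definition, the last one on or before any new therapy).

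DOR (SAP 4.2.4) handles new therapy as the primary PFS definition does. ORR is a proportion and involves no censoring.

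**Step 3. How far deaths help.** The plan expects 741 deaths among 930 participants at the final analysis: 741/930 = 80%. At the interim it is 593/930 = 64%. Under the secondary definition many unconfirmed progressors would therefore become events. Those events would be dated at death, and the missing scans are not recovered.

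**Step 4. Direction of the bias (illustration only).** Inputs: exponential BICR PFS with median 5.0 months in both arms (the EXTREME figure quoted in protocol 1.2), so the true HR is 1.00; scans every 6 weeks; 20,000 per arm; no separate deaths. Assumption: in a fraction q of participants the investigator calls progression one scan before BICR would, scanning stops, and PFS is censored there. This is a strongly informative case.

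| q in A / q in B | HR A/B |
|---|---|
| 0 / 0 | 1.00 |
| 10% / 10%, 20% / 20%, 30% / 30% | 0.99 each |
| 0 / 10% | 1.09 |
| 0 / 20% | 1.18 |
| 0 / 30% | 1.34 |
| 5% / 20% | 1.15 |
| 10% / 30% | 1.25 |

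The Kaplan-Meier median is 5.5 months at q = 0. It is 5.5 or 6.9 at 10%, 6.9 at 20%, and 6.9 to 8.3 at 30%. The steps reflect the scan interval of 42/30.4375 = 1.4 months. Equal rates lengthen the medians but leave the HR near 1. Unequal rates move the HR. Because the two arms have the same true distribution, swapping the rates gives the reciprocals: 1/1.09 = 0.92 and 1/1.34 = 0.75.

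**Step 5. What the SAP would show.** The cross-tabulation in 7.5.5 contains the cell that matters: BICR censored, investigator event. The censoring-reason table in 7.5.4 has no category for unconfirmed investigator progression. Neither gives an effect estimate.

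**The case against.** The strongest reply is that the protocol governs conduct. Section 9.1.1 says the study follows the approved protocol, and the SAP leaves BICR procedures to a charter that is not available here. This has force. A reader might infer that Arm B participants are being kept on chemotherapy after progression; the documents do not show that SAP 2.6 ever reached sites as an instruction. The mismatch between the texts remains.

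Second, SAP 2.6 does not cause the informative censoring. If followed, it would reduce it. The censoring comes from the protocol's scan-stopping rule combined with BICR-based censoring. That is correct, but a safeguard absent from the protocol cannot be relied on.

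Third, scanning does not stop for everyone at investigator progression. Arm A participants treated past progression keep scanning, and equivocal progression is verified by repeat scan (protocol Appendix 3, 3.3.4). Nor is every discordant participant censored, because deaths count as set out in Step 2 and SAP 7.5.4 analyses both PFS definitions. A reader might apply a discordance rate of, say, 10 to 25% to some 800 progressors and arrive at 80 to 200 informatively censored times. Neither input is in the documents, and the product ignores deaths.

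Fourth, a reader might add ORR to the affected endpoints. It has no censoring, and SAP 7.5.1 already repeats it by investigator assessment.

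Finally, PFS, ORR and DOR are estimated without testing (protocol 8.4.2.2, SAP 7.5), so the stakes are limited to secondary estimates.

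**Conclusion.** The contradiction is established from the text alone: direct for Arm B, permitted versus required for Arm A, and internal to the SAP (2.1 against 2.6).

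The effect on BICR PFS and DOR is possible but not quantified. It depends on sites following the protocol, on the investigator's call being the one that stops scans, and on some discordance between readers. The treatment comparison is distorted mainly if the loss of scans differs by arm. That is plausible because only Arm A may continue past progression, but the documents do not establish it. The HRs of 1.09 to 1.34 show what strong assumptions would produce; they do not estimate the bias in this trial. Primary OS, alpha, power and ORR are outside this mechanism.

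**What to change.** 1. Reconcile SAP 2.6 with protocol 3.1, 4.5.6, 5.4 and Tables 5.1-2 and 5.1-3, and with SAP 2.1, so that one rule states whose progression assessment governs stopping treatment and stopping scans, in each arm. Which rule that should be is a clinical matter on which this review takes no position.
2. Add to SAP 7.5.5 a stratified Cox hazard ratio with 95% CI for investigator-assessed PFS.
3. From the cross-tabulation already planned in 7.5.5, report by arm the number of BICR-censored subjects with prior investigator progression. The primary definition shows them most clearly, since later deaths move some to events under the secondary definition.

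The cost is SAP wording or a short protocol clarification, one more Cox model, and a count taken from a planned table.
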